7.2 Study Design

To achieve comparable groups for known and unknown risk factors randomization will be performed as unstratified block randomization with random block sizes in a 1:1 allocation ratio. Allocation to treatment will be carried out by means of a computer-generated random study numbers with group assignment.

Non-randomized cohort

Patients who choose not to be randomized but otherwise meet the inclusion and exclusion criteria will be offered participation in this study as part of a non-randomized cohort. Their data will still be analyzed for the purpose of addressing the secondary objective.

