It is hoped that patients of surgeons that utilize this technology in the preoperative consultation will have significantly higher Breast Q breast augmentation module scores 6 months after surgery. "Satisfaction with care" - one of six core scales within the Breast Q - will be particularly impacted by using 3D image simulation in the consultation experience. Additionally, it is thought that superomedial pole fullness and central nipple position as quantified with mammometrics that

the 3D imaging can provide will be associated with higher Breast Q scores, especially the “satisfaction with breasts” items.

This study will represent one of the first randomized control trials performed to address patient satisfaction with breast augmentation.

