2.2 Secondary Objective

To determine if measureable mammometric parameters are associated with improved patient satisfaction.

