4.2 Randomization

100 patients will be recruited in the randomized cohort. Randomization will be performed by a Research Patient Coordinator and the patient assigned to the control group or the intervention group. Randomization will only occur after the patient has signed the informed consent and will be documented in the case report file as well as communicated to the treating surgeon.

Intervention group

In the intervention group, in addition to standard preoperative evaluation, 3D image simulation will be performed.

Control group

In the conventional group, only the standard preoperative evaluation will be performed.

Non-Randomized cohort

In the non-randomized cohort, the patient can choose to have the standard evaluation with the addition of the 3D image simulation or not based on discussion with their surgeon.

Minimizing measurement bias

Blinding of the patient or surgeon will not be possible due to the need for the 3D imaging simulation to be openly discussed and viewed prior to the operation for patients randomized to 3D intervention and for the nonrandomized cohort.

All subjects will be administered the Breast Q questionnaire prior to surgery regardless of assigned group. The questionnaire will take approximately 5-10 minutes of time to complete.

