7.0 STATISTICAL CONSIDERATIONS

7.1 Study Endpoints

Primary endpoint

BREAST Q Augmentation Module. This includes 6 core items, each with several sub-items. Of the 6 core items, 3 are recently shown to statistically significantly improve in patients undergoing breast augmentation: 1) satisfaction with breasts 2) psychological well-being 3) sexual well being. A fourth, 4) satisfaction with care, however, may be particularly relevant to the discerning aesthetic surgery patient using 3D imaging in consultation. The other core items in this instrument are 5) physical well-being and 6) satisfaction with overall outcome which will also be recorded.

Secondary endpoints

All patients will undergo standard 2D as well as 3D imaging before and after surgery. During consultation, and in the postoperative period, reviewing 3D imaging and morphing software will be unique to the experimental group. 3D imaging from all patients will be used to obtain mammometric data. Pre- , and post- op mammometric data (volumes, vectors, surface distances, anatomic landmarks), as well as the measurable change in these parameters before and after surgery will be correlated with changes in Breast Q patient reported outcomes scores. This will enable us to identify particular mammometric parameters that are a) associated with improved patient reported outcomes and b) determine whether certain mammometric parameters are significantly different in patients who had 3D image simulation as part of their preoperative consultation relative to those that did not.

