7.4 Data Analysis

Data analysis for this study will be descriptive in nature. Demographic and clinical characteristics of the sample, as well as post-surgery complications will be summarized using descriptive statistics and the confidence intervals will also be provided.

[figure not shown]
Patients assigned to the intervention group (3D simulation) will be compared with those who had conventional techniques using χ^2 tests for categorical variables and Student's t-tests for continuous variables. For the t-tests equal variances were not be assumed, unless significant by Levene's test. Mann-Whitney U tests will be utilized for non-normally distributed variables. Two-tailed P values 0.05 will be considered statistically significant.

Multivariate analyses for Breast Q scores, mammometric parameters, and patient satisfaction will be performed using binary logistic regression and linear regression models to examine the relationship between intervention groups and examined outcomes and to identify potential confounders. The results of multivariate analyses will be expressed as odds ratios with corresponding 95% confidence intervals. All analyses will be performed using SPSS 20.0 statistical software (SPSS Inc. Chicago, IL).

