3D Breast Imaging for Cosmetic and Reconstructive Breast Surgery: Does 3D Improve Patient Reported Outcomes in Primary Breast Augmentation?

NCT01964105

AUGUST 27, 2014

The trend of enrolling to the randomized arm of our study will be modeled using the LOGISTIC procedure with maximum likelihood estimation. Predicted probability will be obtained from this model to facilitate clear interpretation of non-linear relationships with time. For patient- level comparisons, the assumption of normality will be examined with the Shapiro-Wilk test after which a t-test or Wilcoxon test will be used as appropriate. When using the t-test, equality of variances will first be examined with the Folded F statistic. The pooled t-test will be used for two populations with equal variances. Otherwise the Satterthwaite t-test will be used. Breast-level comparisons will be performed using generalized estimating equations (GEE) and empirical standard error estimates to account for correlation of left and right breast measurements within the same patient. The Pearson or Spearman correlation coefficient will be used to quantify the direction and magnitude of association between mammometric, Q-Score, and clinical data. Statistical analyses will be performed in SAS, version 9.4, with descriptive statistics analyzed and graphed in Prism 7 for Mac.

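### The secondary association between breast measurements and satisfaction is planned as a plain correlation across differently treated groups, with no term for simulation or cohort

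*Protocol*

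**What the plan says.** - **Objective (Protocol 2.2).** "To determine if measureable mammometric parameters are associated with improved patient satisfaction".
- **Data (Protocol 7.1).** "3D imaging from all patients will be used to obtain mammometric data". Values before and after surgery, and their change, "will be correlated with changes in Breast Q patient reported outcomes scores".
- **Who is included (Protocol 7.2, 7.3).** Besides 100 randomised patients (50 per arm), up to 50 who decline randomisation take part, and of these 7.2 says: "Their data will still be analyzed for the purpose of addressing the secondary objective".
- **How that cohort gets simulation (Protocol 4.2).** "the patient can choose to have the standard evaluation with the addition of the 3D image simulation or not based on discussion with their surgeon".
- **Method (SAP).** "The Pearson or Spearman correlation coefficient will be used to quantify the direction and magnitude of association between mammometric, Q-Score, and clinical data". No covariate, stratum, partial correlation or analysis set is given. The SAP's opening analysis models enrolment to the randomised arm, so its data span both cohorts and cohort membership is known.
- **Regression (Protocol 7.4).** Linear and logistic models are planned for Breast Q scores, mammometric parameters and satisfaction, "to examine the relationship between intervention groups and examined outcomes and to identify potential confounders". The SAP does not repeat these models.
- **Who may have simulation.** Appendix B footnote 3 confines it to patients randomised to intervention, and 7.1 describes 3D review and morphing as unique to the experimental group. Section 4.2 also lets non-randomised patients choose it.

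**The concern.** Simulation could act on both variables being correlated. The protocol hopes that it raises Breast Q scores, and says that satisfaction with care "will be particularly impacted by using 3D image simulation in the consultation experience". Section 1.0 (third question) and endpoint 7.1(b) ask whether it also alters the final dimensions.

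If it does both, and its effect on satisfaction runs partly outside shape (for example through the consultation experience), simulated patients differ from the others in both variables. A coefficient calculated over everyone then contains that difference between groups, even if shape and satisfaction are unrelated within each group. Randomisation does not remove this, because it arises from combining the arms. The non-randomised patients bring a further possible difference: those who seek simulation may differ in expectations and in implant choice.

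At stake is the secondary conclusion. A parameter could be reported as linked to satisfaction when it partly marks who saw the simulation.

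**Working it through.** **1. The plan's own figure.** None is given for the secondary correlation. The nearest is Protocol 7.3: 50 per arm, a 20 percent difference in satisfaction, alpha 0.05 (two-sided by 7.4), power above 99%. The standardised difference that gives 99% power is

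d = (1.960 + 2.326) × √(2/50) = 0.857

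(an exact t calculation gives 0.866). If 20 percent means 20 points on a 0-100 scale, this requires an SD of at most 20/0.857 = 23.3; at SD 25 the power is 97.9%. Read as a 20-point difference in proportions, two-sided power is only 52% to 93%. The stated power therefore fits a comparison of means with an unstated SD and cannot be confirmed. I use 0.86 SD only as a plausible upper satisfaction shift.

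**2. Inputs for the correlation.** From the documents: n = 100 randomised, or 150 with the full non-randomised cohort. Assumed: half of all patients simulated (p = 0.5; the 1:1 allocation gives this for the randomised part only); no association within groups; no cohort difference; shifts d_S (satisfaction) and d_M (mammometric) in within-group SDs, with the path to satisfaction bypassing shape. The documents give no source for either shift.

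**3. Induced correlation.**

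r = p(1−p) d_S d_M / √[(1 + p(1−p) d_S²)(1 + p(1−p) d_M²)]

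Example, d_S = 0.857 and d_M = 0.5: numerator 0.25 × 0.857 × 0.5 = 0.107; denominator √(1.184 × 1.0625) = 1.122; r = 0.096.

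**4. False-positive rate.** By Fisher's z, the test statistic has mean atanh(r) × √(n−3) and unit variance. In the example at n = 150: 0.0959 × √147 = 1.16, so the chance of passing ±1.96 is 21%.

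| d_S | d_M | r | n = 100 | n = 150 |
|---|---|---|---|---|
| 0.86 | 0 | 0.00 | 5% | 5% |
| 0.3 | 0.3 | 0.02 | 5.5% | 5.8% |
| 0.86 | 0.2 | 0.04 | 6.7% | 7.6% |
| 0.5 | 0.5 | 0.06 | 8.9% | 11.0% |
| 0.86 | 0.5 | 0.10 | 15.7% | 21.3% |
| 0.86 | 0.86 | 0.16 | 33.8% | 47.5% |

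Using 0.866 instead of 0.857 raises the last entry to 48.8% and leaves r at 0.16.

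**5. Self-selection.** This was simulated (4,000 runs; 100 randomised plus 50 self-selected, 80% of the latter choosing simulation; shifts 0.86 and 0.5 SD). With no cohort difference, mean r is 0.09 and rejection 19%. If the cohort is also 0.3 SD higher on both variables, r is 0.13 and rejection 36%. If the cohort shifts have opposite signs, r is 0.08 and rejection 16%. Self-selection can therefore add to the component or offset part of it.

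**6. With adjustment.** In the same simulations, the partial correlation given simulation and cohort averaged 0.00, with rejection between 4.6% and 5.6% in every scenario.

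**The case against.** - **Pooling is an inference.** No sentence says that the three groups enter one coefficient, and the SAP sentence is generic. This stands. Still, taking measurements from all patients, including the non-randomised cohort and naming no stratification make it the natural reading.
- **Protocol 7.4 already plans regression.** It does, and nothing in the SAP withdraws it. But its stated aim is the relation between group and outcome, with confounders still to be identified. It does not commit to adjusting the shape-satisfaction association.
- **The association may be real.** If simulation improves satisfaction only by changing shape, the correlation is genuine. This stands: the bias needs a path that bypasses shape. Simulation precedes the surgical result, so adjusting for it does no harm even under full mediation.
- **The affected scale may not be the relevant one.** The protocol expects simulation to act most on satisfaction with care, and mammometrics to relate most to satisfaction with breasts. For the latter the bias may be smaller than shown, although 1.0 hopes for higher module scores generally and 6.3 allows for greater satisfaction with the aesthetic result.
- **The size is modest.** Induced r is at most about 0.16 (about 2.5% of variance) over the range examined, and 7.4 calls the analysis descriptive. This stands and limits the weight of the point.

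Two stronger readings are tempting. A reader might infer that the larger the primary effect, the larger this error. That does not follow: the error depends on the product of both shifts, and the effect on dimensions is an open question in the protocol, not a hypothesis. A reader might also infer from Appendix B that simulation will go unrecorded in the non-randomised cohort. A visit schedule is not a list of form fields, and endpoint 7.1(b), which compares patients with and without simulation, needs that information.

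**Conclusion.** The concern holds in conditional form. The method stated for the secondary objective does not separate a shape-satisfaction association from differences between simulated and unsimulated patients, or between cohorts, and no other passage commits to doing so.

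Whether this matters depends on simulation shifting dimensions, and on it also shifting satisfaction by a route other than shape. The error is negligible at 0.3 SD on both. It roughly doubles the 5% error rate at 0.5 SD on both with 150 patients, and becomes serious only if both shifts are large. The shifts, the share simulated, the absence of a within-group association and the cohort differences are all assumptions. The point merits a change because the remedy is cheap and restores the nominal error rate in every scenario tried, not because the bias is shown to be present.

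Separately, the documents contradict themselves on who may have simulation (Protocol 4.2 against 7.1 and Appendix B footnote 3).

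**What to change.** 1. In the SAP, name the analysis set for the secondary objective. Estimate each association between a mammometric parameter and Breast Q change by partial correlation or regression, with simulation received (yes/no) and cohort (randomised/non-randomised) as covariates.
2. Show the randomised-only estimate, adjusted for simulation, beside the combined one.
3. Reconcile Protocol 4.2, 7.1 and Appendix B footnote 3 on who may have simulation, so that simulation received is coded in the same way for every patient.

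The cost is a few sentences in the SAP, a wording correction in the protocol, and two degrees of freedom out of up to 150 patients. No extra patients, visits or procedures are needed.

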7.3 Sample Size

Appropriate sample size is calculated based on assumption of difference of 20 percent in patient satisfaction as compared with the control group. This difference is considered clinically relevant based on previous similar studies. A sample size of 100 patients (50 in each group) is considered sufficient to prove this difference, if present (alpha error set at 0.05, power>99 percent).

Approximately 75 patients per year undergo a breast augmentation procedure at Washington University Medical Center. The estimated time frame to randomize 100 patients is approximately 24 months.

Non-randomized cohort

Up to 50 patients will be included in the non-randomized cohort.

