Outcomes research in plastic and reconstructive surgery is more likely to focus on patient reported outcomes than survival. While the plastic surgery literature is replete with surveys focused on judging patient satisfaction, they are infrequently validated or comprehensive. The Breast Q has been established as a validated instrument to provide a quantitative measure of the unique features of patient reported outcomes following breast surgery. This instrument represents the most comprehensive and specific quantitative method for patient self-assessment following breast surgery. Recently, McCarthy and colleagues published, for the first time, patient satisfaction in 41 patients who underwent breast augmentation and were evaluated with the Breast Q. This study found statistically significant improvements following breast augmentation in the "satisfaction with breasts" – 14 item scale, "psychological well-being" – 9 item scale, and "sexual well-being" – 5 item scale. This study does not, however, include information on either the benefits of 3D imaging or the mammometric parameters most closely associated with improved satisfaction. Interestingly, the core scale "satisfaction with care" was not evaluated in this study. While this particular core scale may not have been relevant to a study looking at the overall benefits of breast augmentation, we suspect that it may be highly relevant to the aesthetic surgery patient where the consultation experience is more likely to impact overall patient satisfaction.

This study will evaluate the impact of incorporating 3D imaging during preoperative consultation on patient reported outcomes in primary breast augmentation surgery. 3D imaging can be used to facilitate patient education and surgical planning in the context of breast augmentation. The purpose of this study is to utilize the most objective assessment available for assessing patient satisfaction with breast augmentation - the Breast Q - in a prospective randomized trial. We will evaluate whether 3D imaging used in consultation 1) can improve patient reported outcomes, and 2) whether there are measurable mammometric parameters that are associated with improved patient satisfaction and 3) if utilizing 3D imaging in the pre-operative consultation significantly influences final mammometric parameters compared to patients receiving a traditional consultation that does not involve 3D breast surgical simulation.

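### Does the unsupported claim of more than 99% power for a 20 percent difference, with no planned interval in score points, require a change to the plan?

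*Protocol*

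**What the plan says.** Protocol 7.3 gives the sample-size argument in three sentences. The first sets the target: "Appropriate sample size is calculated based on assumption of difference of 20 percent in patient satisfaction as compared with the control group." The second defends its size without naming a source: "This difference is considered clinically relevant based on previous similar studies." The third calls 50 patients per group "sufficient to prove this difference, if present (alpha error set at 0.05, power>99 percent". It contains no scale, SD, control value, test, citation or allowance for loss before the 6-month visit. Section 4.2 recruits the same 100 patients.

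Section 7.1 makes the Breast Q Augmentation Module the primary endpoint and lists six core scales. Section 1.0 expects satisfaction with care to be the scale that "will be particularly impacted by using 3D image simulation in the consultation experience".

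On intervals, section 7.4 says that sample characteristics "as well as post-surgery complications will be summarized using descriptive statistics and the confidence intervals will also be provided". Arms are compared by chi-square, t or Mann-Whitney tests at a two-tailed 0.05. The section then plans logistic and linear regression for Breast Q scores, with results given as odds ratios and 95% intervals. The SAP names a t-test or Wilcoxon test for patient-level comparisons and mentions no interval.

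**The concern.** A power above 99% is unusually high, and none of the inputs needed to reproduce it is given. The stated source is also hard to trace. Section 1.0 describes one Breast Q augmentation study, of 41 patients before and after surgery, and says of it: "This study does not, however, include information on either the benefits of 3D imaging or the mammometric parameters most closely associated with improved satisfaction." It adds that satisfaction with care was not assessed there. It also says of the present trial: "This study will represent one of the first randomized control trials performed to address patient satisfaction with breast augmentation."

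The worry is how a null result would be read. A P value above 0.05, set beside the claim in 7.3, invites the conclusion that a 20 percent benefit has been ruled out. If the scores vary more than the planners supposed, the data may still be compatible with 20 percent. A report giving only P values would not show this, and an inconclusive trial could pass as a negative one.

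**Working it through.** **Inputs.** From the protocol: 50 per arm, 1:1 allocation, alpha 0.05 two-sided (7.2 to 7.4), a difference of 20 percent, power above 99%. My assumptions: the SDs, the control values, and 40 evaluable per arm (20% loss). Let B be the quantity of which the 20 percent is taken: the control mean if relative, the scale range if absolute.

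**1. The plan's own figure.** It cannot be reproduced without an SD, so I solve for the SD at which it holds. Two-sample t-test, noncentral t, noncentrality d × √(n/2), where d is the difference in SD units:

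| Evaluable per arm | d for 80% power | d for 90% | d for 99% | Largest SD for 99% = 20/d |
|---|---|---|---|---|
| 50 | 0.566 | 0.655 | 0.866 | 23.1% of B |
| 40 | 0.634 | 0.734 | 0.971 | 20.6% of B |

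The claim is attainable but conditional. If the 20 percent is relative and the control mean is 60 points (assumed), the SD must be at most 0.231 × 60 = 13.9 points.

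**2. Power if the SD is larger.**

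| SD, % of B | 50 per arm | 40 per arm |
|---|---|---|
| 20 | 99.9% | 99.3% |
| 25 | 97.7% | 94.2% |
| 30 | 91.0% | 83.8% |
| 40 | 69.7% | 59.8% |

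Power of 80% is kept up to an SD of 20/0.566 = 35.3% of B with 50 per arm, and 20/0.634 = 31.5% with 40.

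**3. When a null result can still contain 20 percent.** The 95% half-width is h = t(0.975, 2n−2) × SD × √(2/n), which is 0.397 SD with 50 per arm and 0.445 SD with 40. A non-significant result needs an observed difference below h. An interval that reaches 20 needs an observed difference of at least 20 − h. Both are possible only if h exceeds 10, so the observed SD must exceed 10/0.397 = 25.2% of B (50 per arm) or 10/0.445 = 22.5% (40 per arm). Both limits lie above the SDs at which the 99% claim holds (23.1% and 20.6%).

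**4. How often that happens.** The observed SD varies around the true one, so I simulated the difference and the pooled SD with 50 per arm. The table gives the share of trials that are non-significant with an interval still containing 20 percent:

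| True SD, % of B | True difference 0 or 20% | True difference 10% |
|---|---|---|
| 23 | below 0.1% | about 0.5% |
| 30 | about 6 to 7% | about 24% |
| 40 | about 27 to 28% | about 53% |

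With 40 per arm and an SD of 20.6% of B, the largest share over true differences from 0 to 20% is about 0.8%.

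**5. If a proportion was meant.** Exact enumeration of the uncorrected chi-square test, 50 per arm, 20 percentage points: 55% for 50 v 70%, 73% for 70 v 90%, 85% for 75 v 95%, and 99.4% for 80 v 100%. Only the boundary case reaches the stated power.

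**6. Where an interval in points would come from.** A t-test already yields the difference in means and its standard error. Section 7.4 also plans linear regression of Breast Q scores on group, and that group coefficient is a difference in points. A linear model cannot produce an odds ratio, so the reporting sentence in 7.4 is loose drafting that fits only the logistic models.

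**The case for a change.** The strongest reply is that a plan should not depend on goodwill. Neither document commits to an effect estimate in points. Read literally, 7.4 expresses every multivariate result as an odds ratio, and a Wilcoxon P value brings no interval with it. The word *prove* in 7.3 overstates what a test can show, and one added line per scale would cost nothing. Part of this stands. The sample-size paragraph is thin, it has no citation, and it makes no allowance for loss.

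The proportion reading also has some footing. Section 7.4 lists patient satisfaction beside Breast Q scores and plans binary logistic regression, and under that reading the power claim fails at most control rates. Against it, 7.1 makes the Breast Q scales the endpoint, no cut-off for a satisfied patient is defined anywhere, and the SAP's patient-level tests are the t-test and the Wilcoxon.

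The argument about the source does not stand. Section 7.3 cites earlier studies for what difference is clinically relevant, not for an observed effect of 3D simulation. A relevance threshold needs no earlier 3D study and no earlier randomised trial. Only the missing citation is left.

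**Conclusion.** No change to the plan follows. The power statement lacks detail but is not shown to be wrong. Read as a difference in mean score, it holds up to an SD of 23.1% of B with 50 evaluable per arm (20.6% with an assumed 40). In that range a null result that leaves 20 percent open occurs in under 1% of trials. Beyond it the risk is real, about 24% at worst with an SD of 30% of B and 50 per arm, but the documents give no reason to expect an SD that large, and power there is still 91.0%.

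Rewording 7.3 would alter neither the number of patients, the allocation, the alpha nor the tests, and without an SD the new sentence would be as conditional as the old one. The interval in points is ordinary output that a competent analyst would report from the planned analyses, and a null result will be judged on that interval and not on the design-stage power. No passage says that a null result will be reported as no benefit.

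This conclusion assumes that the 20 percent refers to a mean score, as the endpoint in 7.1 suggests. If a proportion was meant, the stated power would be too high except near 80 v 100%.
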